The primary and secondary variables will be analysed using geometric means. Both the difference in number and the % change or ratio will be reported, but the statistical analysis will only be based on the ratio. All hypothesis testing will be reported using 2-sided tests. P-values will be rounded to 4 decimal places. No adjustment for multiplicity will be performed and nominal p-values will be reported.

For the efficacy analyses except PRO/ SNOT-20 data, if the value of the ratio of Week 12 to baseline is zero and both Week 12 and baseline are not missing, the ratio will be replaced, for the analysis of ratio only (including for descriptive statistics), by half the smallest observed ratio among the randomized subjects with non-zero values (both treatment arms). For the corresponding non descriptive analyses on the ratio, values of baseline equal to zero were replaced by half the smallest observed value among the subjects with non-zero for the calculation of the baseline logtransformed covariate,

For the efficacy analyses except PRO/ SNOT-20 data, if the baseline value is zero, the baseline will be replaced, for the analysis of ratio to baseline or percent change from baseline only (including for descriptive statistics), by half the smallest observed value among the randomized subjects with non-zero values and among all records (baseline and post baseline

for both treatment arms). If both the baseline and post-baseline record are zero, then the percent change is zero.

QQ plots of residuals of the primary and secondary efficacy analysis models (both on absolute change and log-transformed ratio) will be created.

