#### 4.1.1 Sensitivity analyses

An ANCOVA will be done on raw data (no log-transformation) with the absolute change from baseline as response variable. The model will include treatment group as fixed effect and baseline value as a continuous covariate. No interaction terms will be included in the model.

To investigate the sensitivity to the Normality assumption in the Primary analysis, a nonparametric analysis of covariance (ANCOVA) model on the ranks of the absolute change from baseline at Week 12 (Visit 9) sensitivity analyses for the primary endpoint will be performed. Tied values will receive the mean values of the corresponding ranks.

A further sensitivity analysis of the ANCOVA based on ranks will be conducted based on the same model of the initial ANCOVA based on ranks, but using the ratio as response. The same replacement rule for ratio described above in section 4.1 will be applied for zero values.

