This approach assumes that no subject has a missing baseline result. If there are subjects with missing baseline results, a regression imputation will be used first, with missing baselines being replaced by their predicted values, given the other baseline covariates (apart from treatment group).

A further sensitivity analysis of the primary efficacy analysis will be done removing the subjects who have a subject with a baseline value=0 or a week 12=0.

As per section 3.1.4, week 12 records not collected within study days 78-99 will not be analyzed as part of the primary efficacy. A further sensitivity analysis of the primary efficacy will be done keeping the subjects with the week 12 records falling outside of the week 12 window.

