## 4.2.4 Analysis of the primary variable

All analyses of the primary endpoint will be based on the FAS.

The primary efficacy variable is the change, expressed as a ratio [Week 12 (Visit 9)/baseline] from baseline to Week 12 (Visit 9) in airway submucosal eosinophils and the primary analysis is to compare this change from baseline to Week 12 (Visit 9) for tralokinumab with placebo.

The primary efficacy variable will be evaluated through the hypothesis test:

H0: ratio (tralokinumab/placebo) equals 1 *vs*. H1: ratio does not equal 1.

The null hypothesis  $(H_0)$  is that the change in airway submucosal eosinophils at Week 12 on tralokinumab is equal to the corresponding change on placebo. The alternative hypothesis  $(H_1)$  is that the change in airway submucosal eosinophils during the 12-week double-blind treatment period is different on tralokinumab compared with the change in airway submucosal eosinophils during the 12-week double-blind treatment period on placebo.

The change in airway submucosal eosinophils in the tralokinumab group will be compared to that seen in the placebo group using an ANCOVA model.

The response variable in the model will be change, on the log-scale (expressed as a ratio) in the number of airway submucosal eosinophils from baseline to Week 12 (Visit 9) [Week 12 (Visit 9)/baseline]. The model will include treatment group as fixed effect and baseline log value as a continuous covariate. No interaction terms will be included in the model. The analysis will be performed using log-transformed data. All group comparisons from ANCOVA model will be based on Type III sums of squares. Estimated geometric means (original scale) will be presented for each treatment group as well the ratio of geometric means for the comparison of tralokinumab versus placebo (tralokinumab/placebo) and corresponding 95% confidence interval (CI).

Available values at both baseline and Week 12 (Visit 9) are required for a subject to be included in the analysis.

Summary statistics for the absolute and percentage change from baseline to Week 12 (Visit 9) will also presented.

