#### 4.2.5.1 Blood eosinophil count

**The secondary outcome variable blood eosinophil count is:** Change, expressed as a ratio [Week12 (Visit 9)/baseline], from baseline in the blood eosinophil count to Week 12 (Visit 9).

The change from baseline to Week 12 (Visit 9) in blood eosinophil count will be compared between tralokinumab and placebo using a mixed model for repeated measures (MMRM) with treatment group, logbaseline and visit as fixed effects. Treatment-by-visit interaction will also be included. The analysis will be performed by using log-transformed data on all post baseline visits during treatment phase.

The response variable will be the change, on the log-scale (expressed as a ratio) in blood eosinophil count from baseline to Week 12 (Visit 9) [Week 12 (Visit 9)/baseline]. A restricted maximum likelihood (REML) approach will be used. All subjects with a baseline blood eosinophil count in the FAS will be included in the analysis. An unstructured variance-covariance matrix will be used to model the within-subject errors. If the model fails to converge then a compound symmetric variance-covariance matrix will be used instead. The Kenward-Roger approximation will be used to estimate denominator degrees of freedom.

Estimated geometric means ratios (original scale) will be presented for each treatment group as well the ratio of geometric means ratios for the comparison of tralokinumab versus placebo (tralokinumab/placebo) and corresponding 95% CI.

An MMRM will also be done on raw data (no log-transformation) with the absolute change from baseline as response variable. The model will include treatment group as fixed effect baseline value, and visit as fixed effects. Treatment-by-visit interaction will also be included.

Summary statistics for the absolute change from baseline at all visits in blood eosinophil count will be presented by treatment group.

Blood eosinophil count and absolute change from baseline will also be listed. 4.2.5.2 Differential sputum eosinophils

**The secondary outcome variable differential sputum eosinophils is:** Change, expressed as a ratio [Week12 (Visit 9)/baseline], from baseline in differential sputum eosinophils to Week 12 (Visit 9)

This will be analysed and summarised as described for blood eosinophil count in Section 4.2.5.1.

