- Section 4.1: Clarified analyses of percent change and ratio when baseline and / or post-baseline=0.
- Added further sensitivity analysis on sponsor request.

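### A subject with zero submucosal eosinophils at both biopsies is given the joint-lowest ratio in the trial, although SAP 4.1 scores the same subject as 0% change

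*SAP*

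**What the plan says.** SAP 4.1 has three relevant rules for efficacy variables.

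- Zero baseline: "if the baseline value is zero, the baseline will be replaced" for ratio and percent change, by half the smallest non-zero value among all baseline and post-baseline records in both arms. Call this value c.
- Zero ratio: when the Week 12 to baseline ratio is zero and neither value is missing, the ratio is replaced "by half the smallest observed ratio among the randomized subjects with non-zero values (both treatment arms".
- Both zero: "If both the baseline and post-baseline record are zero, then the percent change is zero". The sentence mentions percent change only; no counterpart is given for the ratio.

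The order of the first two rules is not stated. SAP 4.1 bases statistical testing on the ratio alone, and SAP 3.1.2 requires a log transformation for it. SAP 4.2.4 fits an ANCOVA of the log ratio on treatment and log baseline, with this inclusion rule: "Available values at both baseline and Week 12 (Visit 9) are required for a subject to be included in the analysis".

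SAP 4.1.1 carries the rule into the rank ANCOVA on the ratio: "The same replacement rule for ratio described above in section 4.1 will be applied for zero values". It also plans a primary sensitivity analysis "removing the subjects who have a subject with a baseline value=0 or a week 12=0". SAP section 6 lists the topic as a change from the protocol: "Clarified analyses of percent change and ratio when baseline and / or post-baseline=0".

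**The concern.** One section scores one subject in two opposite ways. On percent change the subject is unchanged; on the tested scale the subject is tied with the best responders. By the definitions in SAP 3.1.2, percent change equals 100 × (ratio − 1), so 0% corresponds to a ratio of 1.

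The replacement feeds the primary ANCOVA, the rank ANCOVA on the ratio and the secondary log-ratio models. An extreme value in each arm inflates the residual variance and costs power. Unequal numbers between arms move the estimate, in a direction that depends on the arm. No eligibility criterion sets a minimum eosinophil count, so such subjects can be randomized.

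Two smaller gaps sit beside this:

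- The zero-ratio rule names Week 12 only, whereas for the secondary MMRMs "The analysis will be performed by using log-transformed data on all post baseline visits during treatment phase".
- The zero-baseline replacement is worded differently for the log-baseline covariate and for the denominator, so two values are possible.

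**Working it through.** **The plan's own figure.** Inputs from SAP 1.3 and Protocol 8.2: SDs of log values 1.62 and 1.82, 3.5-fold difference, two-sided 5%, 31 per arm. Pooled SD = √((1.62² + 1.82²)/2) = 1.723 and ln 3.5 = 1.253. Power from the noncentral t is 79.1% at 30 per arm and 80.4% at 31. The smallest significant difference is exp(t₀.₉₇₅,₆₀ × 1.723 × √(2/31)) = 2.40-fold. Both planned figures reproduce.

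**The order of the rules.** With the baseline rule first, 0-to-0 gives 0/c = 0, and the zero-ratio rule then applies. With the zero-ratio rule first, 0/0 is undefined and the rule is not triggered. The later baseline replacement leaves a ratio of 0, which has no log, so a subject with both values would be lost despite SAP 4.2.4. Only the first order gives an analysable value.

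**Illustration.** Take (baseline, Week 12) = (20,10), (8,2), (40,1), (12,0), (0,6), (0,0), (5,5). Then c = 1/2 = 0.5, the smallest non-zero ratio is 1/40 = 0.025, and the replacement is 0.0125.

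| Subject | Ratio analysed | Log ratio | Percent change |
|---|---|---|---|
| (12,0) | 0.0125 | −4.38 | −100% |
| (0,0) | 0.0125 | −4.38 | 0% |
| (5,5) | 1 | 0 | 0% |

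**Shift per subject.** Suppose there is no true effect, 31 per arm and a typical substituted ratio of 0.0097. One 0-to-0 placebo subject moves the placebo mean log by ln(0.0097)/31 = −4.64/31 = −0.150. The treatment ratio becomes exp(0.150) = 1.16 instead of 1.00.

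**Simulation of the primary ANCOVA.** 4,000 runs per cell, 31 per arm, the planned SDs, true ratio 1/3.5 = 0.286. Assumptions not in the documents: baseline log SD 1.3, slope of log ratio on log baseline 0 to −0.8, and the number of 0-to-0 subjects. The documents do not say which arm has which SD. Power with one 0-to-0 subject in each arm:

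| Slope | As written | 0-to-0 ratio = 1 | Loss (points) |
|---|---|---|---|
| 0 | 73.5% | 78.6% | 5.1 |
| −0.3 | 71.1% | 80.0% | 8.9 |
| −0.5 | 70.3% | 82.7% | 12.4 |
| −0.8 | 74.3% | 90.2% | 15.9 |

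- Two per arm: loss of 8 to 28 points.
- One in placebo only: loss of 13 to 24 points.
- One in tralokinumab only: −0.3 to +5 points, the gain coming from bias.
- Treatment ratio, equal numbers per arm: unmoved (0.30 under both rules).
- Treatment ratio, 4 tralokinumab and 2 placebo: 0.25–0.29 as written, 0.30–0.33 with ratio 1.
- Treatment ratio, 2 tralokinumab and 4 placebo: 0.35–0.40 as written, 0.31–0.35 with ratio 1.
- Rank ANCOVA on the ratio, one per arm (2,000 runs): loss of 3 to 7 points.
- Substituted ratio: 0.0042 to 0.0047 on average, that is 1/0.0047 ≈ 210-fold to 1/0.0042 ≈ 240-fold.

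**Chance zeros.** With Poisson counts (median 5, 10 or 20 over 1 mm²), rescoring 0-to-0 as 1 changes power by −2.0 to +0.9 points.

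**Type I error.** In the ANCOVA it was 1.3% to 5.1% for 1 v 1, 2 v 2, 4 v 2 and 2 v 4. In a simpler two-sample t-test with all such subjects fixed in one arm, null rejection was about 5% for one, 7.4% for two in placebo and 11.7% for three in placebo. Those are rates conditional on a lopsided split. Under no effect the arm of each such subject is decided by randomization, so this is not an overall inflation.

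**The case against.** The strongest points on the other side are these.

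1. The SAP does not fix the order, raw 0/0 is undefined, and a programmer could carry the 0% rule over to a ratio of 1. This stands as a description of an ambiguity. But the carry-over is not written, and the only order that works literally gives the joint-lowest ratio.

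2. The power losses come from subjects placed in the simulation. No frequency is given, Protocol 1.2 selects uncontrolled asthma to make raised submucosal eosinophils more likely, and chance zeros cost almost nothing. This stands in full, and the size must be read as conditional.

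3. The planning SDs may already contain zeros from the earlier biopsy studies, so adding 0-to-0 subjects may count that spread twice. Holding the overall SD near 1.71, power as written is 82.9% at slope 0 and 80.0% at slope −0.5, so the planned 80% survives. Gaps of 4 and 11 points to the ratio = 1 rule remain.

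4. Other analyses are planned. The two absolute-change ANCOVAs score 0-to-0 as no change, and residual plots would show the outlier. But the absolute-change analyses do not estimate the ratio. The zero-exclusion analysis also drops subjects whose eosinophils cleared by Week 12, so it selects on the outcome. None repairs the primary result.

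5. Protocol 8.5.1 already prescribes half-minimum replacement for a zero change, and ratio = 1 is also a convention. True, but it is the convention that the SAP itself adopts for percent change.

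**Conclusion.** The concern holds. As written, SAP 4.1 enters no change as the joint-lowest ratio on the only scale that is tested, and contradicts its own percent-change rule. Confidence in that reading is high.

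Its impact depends on how many subjects are truly at zero at both visits, which the documents do not give. Under the stated assumptions, one such subject per arm costs 5 to 16 points of power, and unequal numbers can move the treatment ratio either way. If zeros are only sampling chance, the effect is about nil. Overall Type I error is not the issue. The point should be settled before unblinding, because a later choice could look outcome-driven. The two smaller wording gaps were not quantified.

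**What to change.** In SAP 4.1:

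- State that when baseline and post-baseline are both zero the ratio is 1 (log ratio 0), applied before the zero-ratio replacement.
- Apply the zero rules at every post-baseline visit analysed.
- Use one stated replacement for a zero baseline in both the denominator and the log-baseline covariate.

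Record the exception in SAP section 6, since Protocol 8.5.1 does not contain it.

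In SAP 4.1.1, add or substitute an exclusion analysis based on baseline zero only. In the Poisson runs (true effect 3.5-fold), excluding Week 12 zeros as well gave 2.5- to 3.2-fold. Replacing all zeros by one common count is a possible further sensitivity analysis. It gave 2.7- to 3.6-fold, against 3.4- to 4.2-fold with 0-to-0 set to 1, so it usually pulls the estimate towards no effect. These additions are optional.

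The cost is a few sentences, one entry in SAP section 6 and a few program lines. No new data are needed.

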#### 4.1.1 Sensitivity analyses

An ANCOVA will be done on raw data (no log-transformation) with the absolute change from baseline as response variable. The model will include treatment group as fixed effect and baseline value as a continuous covariate. No interaction terms will be included in the model.

To investigate the sensitivity to the Normality assumption in the Primary analysis, a nonparametric analysis of covariance (ANCOVA) model on the ranks of the absolute change from baseline at Week 12 (Visit 9) sensitivity analyses for the primary endpoint will be performed. Tied values will receive the mean values of the corresponding ranks.

A further sensitivity analysis of the ANCOVA based on ranks will be conducted based on the same model of the initial ANCOVA based on ranks, but using the ratio as response. The same replacement rule for ratio described above in section 4.1 will be applied for zero values.

It is likely that some biopsy specimens will not be evaluable. Although some subjects will have missing data for other reasons, it is envisaged that the invasive nature of the biopsy procedure will directly result in some missing biopsy outcomes. Such biopsy-related missing pattern is likely not to be informative about the potential outcome – that is, such data is likely to be missing at random (MAR). The following sensitivity analysis for the primary and the secondary endpoints will be used to explore the robustness of the analyses to assumptions about this missing biopsy data. This sensitivity analysis will take account of the potential difference between biopsy-related missingness (arguably MAR) and other sources of missing data. A subject will be counted as having biopsy-related missing outcome if the biopsy outcome is missing at Week 12, but other Week 12 data was collected for the subject. In the sensitivity analysis implemented by multiple imputation (MI), biopsy-related missingness will be imputed assuming MAR. All other missing values will be imputed with the"Dropout Reason-based Multiple Imputation (DRMI)": Missing counts will be imputed differently depending on the reason for dropout; counts for subjects in the Tralokinumab arms who dropped out for a treatment related reason are imputed based on the expected event rate in the placebo arm  $(p_{T2} = p_{P1})$ , whereas the remaining subjects who have dropped out are imputed assuming MAR. Treatment related reasons include (1) AEs, (2) Death (3) development of study specified reasons to stop active treatments and (4) severe non compliance.

The data will be log-transformed before the imputation process begins, and the ratio of each scheduled visit to baseline visit will be the variable of interest for imputation. The missing ratio at Week 12 (Visit 9) will be imputed using regression imputation (using MONOTONE REG option of SAS PROC MI). 100 imputations will be carried out, and a seed of 221014 will be used. The analysis of each of the imputed datasets will be as described for the primary

analysis in Section 4.2.4 and these will be combined using SAS procedure PROC MIANALYZE and results presented as per the primary analysis.

This approach assumes that no subject has a missing baseline result. If there are subjects with missing baseline results, a regression imputation will be used first, with missing baselines being replaced by their predicted values, given the other baseline covariates (apart from treatment group).

A further sensitivity analysis of the primary efficacy analysis will be done removing the subjects who have a subject with a baseline value=0 or a week 12=0.

As per section 3.1.4, week 12 records not collected within study days 78-99 will not be analyzed as part of the primary efficacy. A further sensitivity analysis of the primary efficacy will be done keeping the subjects with the week 12 records falling outside of the week 12 window.

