## 3.9.2 Post-randomization

After randomization and receiving IP, subjects are free to discontinue IP and withdraw from the study at any time without prejudice to further treatment. A subject that decides to discontinue the IP and withdraw from the study will always be asked about the reason(s) for their decision to withdraw and the presence of any AEs. If possible, they will be seen and assessed by an Investigator(s). Adverse events will be followed up (as described in Section 6.3).

Subjects will be withdrawn from the study in the following situations:

- 1. Subject decision. The subject is at any time free to discontinue treatment, without prejudice to further treatment
- 2. The subject experiences an AE that, in the opinion of the Investigator, contraindicates further dosing
- 3. The development of any risk to the subject as judged by the Investigator or AstraZeneca
- 4. Severe non-compliance with the study protocol as judged by the Investigator or AstraZeneca
- 5. Pregnancy

6. Lost to follow-up¹

- 7. Development of any study specific criteria for discontinuation, including:
  - a) An anaphylactic reaction to the IP requiring administration of epinephrine
  - b) A helminth parasitic infestation requiring hospitalization
  - c) An asthma-related event requiring intubation
  - d) Any malignancy
- 8. Development of one or more of the following:
  - a) Confirmed ALT or AST increase of  $\geq 8 \times ULN$
  - b) Confirmed ALT or AST increase of  $\geq 5 \times ULN$  for more than 2 weeks
  - c) Confirmed ALT or AST increase of  $\geq 3 \times ULN$  and total bilirubin of  $\geq 2 \times ULN$
  - d) ALT or AST of  $\geq$ 3 x ULN with the appearance of fatigue, nausea, vomiting, right upper quadrant pain or tenderness, fever, rash, and/or eosinophilia ( $\geq$ 5%)

The Principal Investigator will perform all the possible observation(s), test(s) and evaluation(s) including completion of questionnaires if any, as per End of Treatment (EOT) assessments mentioned in Table 1 as soon as possible. Investigator will give appropriate medication and take all possible measures for the safety of the subject. They will also immediately inform AstraZeneca of the withdrawal. Subject will then be followed up for additional 16 weeks from the last dose of IP, unless the subject withdraws consent for any further follow-ups. During follow-up, the Investigator will perform all possible assessments in accordance with schedule provided in Table 1.

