#### 3.1.4 Visit and period windows

For local laboratory data, vital signs, physical examination, and ADA, the visit recorded in the Web Based Data Capture system will be used.

For the efficacy assessments, central laboratory results, spirometry, ACQ-6 and SNOT-20, the variables will be summarized based on the scheduled days with adjusted analysis-defined visit windows as defined in Table 1.

Any data collected at unscheduled visits will be listed, included within baseline data in shift plots, and will be included in the definition of maximum/ minimum within-period value, but will not be included in summaries by visit. In case of a missing assessment at a scheduled visit followed by an unscheduled visit, the unscheduled assessment will not replace the missing result in the summary outputs by period and visit.

If appropriate, i.e. if a substantial percentage of observations for a secondary efficacy variable falls outside the adjusted window, a sensitivity analysis will be performed where observations are assigned according to the extended windows in Table 1.

Visit	Target Day	Adjusted windows for analyses:	Extended windows for sensitivity analyses: Blood eosinophils count; Differential sputum eosinophils; Blood eosinophils and sputum free ECP
Baseline (Week 0) a	1	1	1
Week 2	15	2-21	-
Week 4	29	22-35	-
Week 6	43	36-49	2-63
Week 8	57	50-63	-
Week 10	71	64-77	-
Week 12	85	78-99	64-99
Week 16 (FU1)	113	100-147	-
Week 26 (FU2)	183	148-217	

Table 1Visit windows

If the Day 1 assessment is missing, see section 3.1.1 on how baseline value is defined.

For assignment of data to time points using the visit windows, study day will be defined as follows for efficacy data:

(Date of assessment - Date of randomisation) + 1.

And as follows for safety endpoints:

(Date of assessment - Date of first dose of IP) + 1.

In case of multiple observations within a single visit window, the following rules apply:

- If there are two or more observations within the same visit window, the non-missing observation closest to the target day will be used in the analysis
- If two observations are the same distance from the target day, the non-missing observation with the earlier collection date will be used in the analysis
- If two observations are collected on the same day and have a collection time associated with them, the non-missing observation with the earlier collection time will be used in the analysis

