# 4.2 Analysis methods

### 4.2.1 Subject disposition, demography data and subjects characteristics

Subject disposition will be summarized using the All subjects analysis set.

The number of enrolled subjects will be summarized. The number and percentage of subjects within each treatment group will be presented by the following categories; randomized, not randomized (and reason), received IP, did not receive IP (and reason), completed treatment, discontinued treatment (and reason), completed study, and discontinued study (including reason).

The number and percentage of subjects, who discontinued IP, but remained in the study will be presented by treatment group and will also be listed.

Demographic data such as age, gender, ethnicity and race will be summarized by treatment group for the FAS.

Various baseline characteristics will also be summarized by treatment for the FAS. These include medical, surgical and respiratory disease histories, asthma related events in the past 12 months, weight, height and BMI, use of nicotine (never/ former/ current), asthma duration (defined as date of informed consent – date of diagnosis), age at onset of asthma (defined as date of diagnosis – date of birth), asthma medications (using fluticasone as reference medication), the number of asthma exacerbations in the previous 12 months and number of asthma exacerbations in the previous 12 months.

Medical and surgical histories will be summarized by MedDRA Preferred Term (PT) within the System Organ Class (SOC) level of MedDRA version 20.0.

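### The missing-biopsy imputation checks for other Week 12 data before the reason for stopping, so some tralokinumab subjects with a treatment-related stop escape the placebo-based step

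*SAP*

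**What the plan says.** SAP 4.1.1 sorts missing Week 12 biopsies in two steps.

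1. A subject is "counted as having biopsy-related missing outcome if the biopsy outcome is missing at Week 12, but other Week 12 data was collected". For this class, "biopsy-related missingness will be imputed assuming MAR".
2. "All other missing values will be imputed with the" dropout-reason method. Under it, tralokinumab subjects who "dropped out for a treatment related reason are imputed based on the expected event rate in the placebo arm", and other dropouts are imputed under MAR. "Treatment related reasons include (1) AEs, (2) Death (3) development of study specified reasons to stop active treatments and (4) severe non compliance".

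Step 1 does not consider whether the subject was still on investigational product (IP), why IP was stopped, or whether a biopsy was attempted. Nothing in the section lets the reason override it.

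Other sections bear on who can fall into step 1:

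- SAP 4.2.1 (disposition): "The number and percentage of subjects, who discontinued IP, but remained in the study will be presented by treatment group". SAP 4.1 keeps data collected after IP is stopped.
- Protocol 3.9.2: a withdrawn subject is assessed "as per End of Treatment (EOT) assessments mentioned in Table 1 as soon as possible" (EOT is Visit 9, Week 12, in that table). Follow-up then continues to 16 weeks from the last dose, unless consent for it is withdrawn.
- SAP 3.1.4: most efficacy and central laboratory data count as Week 12 only on days 78-99. However, "For local laboratory data, vital signs, physical examination, and ADA, the visit recorded in the Web Based Data Capture system will be used".

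The SAP does not define what counts as other Week 12 data.

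**The concern.** The SAP says this analysis is meant to separate gaps caused by the biopsy procedure from other gaps. The presence of other Week 12 data does not make that separation. A subject who stopped IP for an AE, came to Visit 9 and had no bronchoscopy is classed with a subject whose specimen failed.

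Protocol 8.5.5 says that informative missingness cannot be ruled out and promises a range of assumptions. The placebo-based step is the only non-MAR assumption the SAP specifies. The other sensitivity analyses change the response scale, use ranks, drop zeros or widen the visit window. For subjects diverted from the placebo-based step, the analysis could appear to confirm robustness without having tested it.

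**Working it through.** **What the step 1 test changes.** Comparing the imputation each type of subject receives with and without the test:

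| Subject with missing Week 12 biopsy | With the test | Without it |
|---|---|---|
| Placebo arm, any reason | MAR | MAR |
| Tralokinumab, no stop for reasons (1)-(4) | MAR | MAR |
| Tralokinumab, stop for (1)-(4), no other Week 12 data | placebo-based | placebo-based |
| Tralokinumab, stop for (1)-(4), some other Week 12 data | MAR | placebo-based |

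The last row assumes that stopping for reasons (1)-(4) counts as dropping out, whether the subject left the study or only stopped IP. The SAP does not say whether stopping IP alone counts. On that assumption, the test's only effect is to remove the last group from the placebo-based step.

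**Who is in that group.** This depends on how Week 12 data are read.

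- *Days 78-99.* SAP Table 1 puts the Week 8 and Week 10 visits at target days 57 and 71. An EOT visit after a Week 8 last dose must come at least 78 - 57 = 21 days later to count; after a Week 10 last dose, 78 - 71 = 7 days later. The group is mainly late stoppers and those followed up to Week 12.
- *Recorded visit.* If an early EOT visit entered as Visit 9 counts, through vital signs, physical examination, local laboratory data or ADA, the group could include most AE withdrawals who attend that visit.

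**The plan's own figure.** Inputs are log SDs of 1.62 and 1.82, a 3.5-fold difference, two-sided 5% and 1:1 allocation (SAP 1.3).

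- SD = sqrt((1.62² + 1.82²)/2) = 1.723; ln(3.5) = 1.253.
- Power from the noncentral t is 79.1% at 30 per arm and 80.4% at 31, so 31 is reproduced.
- The smallest significant difference at 31 per arm is 2.40-fold, matching the 2.4 in protocol 8.2.

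**Size of the shift.** Let k of the 40 tralokinumab subjects be in the last row of the table. k is an assumption. Biopsies are scheduled only at baseline and EOT, so no interim biopsy informs the imputation. The SAP does not list the imputation covariates. I assume treatment and log baseline, the primary model's terms.

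- MAR for all: the expected log effect stays at ln(3.5), or 3.50-fold, essentially the complete-case result.
- Placebo-based for the k: their expected effect is zero, so the arm effect is ln(3.5) × (1 - k/40).

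| k | Log effect | Fold difference | Relative to 3.50 |
|---|---|---|---|
| 1 | 1.253 × 0.975 = 1.221 | 3.39 | 3% smaller |
| 2 | 1.253 × 0.950 = 1.190 | 3.29 | 6% smaller |
| 4 | 1.253 × 0.900 = 1.127 | 3.09 | 12% smaller |

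**Simulation check.** This used 1,000 trials, 30 imputations, Rubin's rules and 9 of 40 missing per arm, with baseline unrelated to change.

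- k=2: 3.54-fold under MAR against 3.25 placebo-based; power 80% against 75%.
- k=4: 3.48-fold against 3.10; power 79% against 73%.
- k=0, where the two rules are identical: 3.52 against 3.42, and 78% against 77%. This shows the Monte Carlo noise (standard error of each power about 1.3 to 1.6 points).

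**The case against.** The strongest reply is that the affected group may be small.

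- On the day 78-99 reading, AE withdrawals seen before day 78 with no later Week 12 data still reach the placebo-based step, as do deaths before Week 12.
- Protocol 3.9.2 lists an AE contraindicating dosing, severe non-compliance and the study-specific criteria as grounds for withdrawal from the study. The disposition row for stopping IP but staying in the study does not mention AEs.
- The gap between 40 randomised and 31 needed is attributed to failed biopsies, and protocol 1.3 reports good tolerability. The nine subjects per arm cannot be read as k.

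All of this stands, and it limits the number affected. It does not alter the order of the two rules, and the required EOT assessments and follow-up make such subjects foreseeable.

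A second reply is that late stoppers are not fully placebo-like. Protocol 3.8 equates 16 weeks with five half-lives, or 3.2 weeks each. A subject last dosed at Week 8 is two weeks further from dosing at Week 12 than one dosed at Week 10, with about 0.5^(2/3.2) = 65% of the exposure (first-order decline, accumulation ignored). This is fair. The figures above compare two imputation rules and do not measure bias against the truth. The placebo-like value is the SAP's own choice for these reasons.

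Third, the analysis that keeps out-of-window Week 12 records may bring in some observed biopsies from early EOT visits. That helps, but it is not a missing-not-at-random analysis.

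A reader might infer that AE stoppers are imputed as on-drug responders. The documents do not support that: MAR draws from all observed tralokinumab values, whatever the response, and these can include subjects who stopped IP and still had a Week 12 biopsy. A reader might also infer that the placebo-based route is left mainly to subjects lost to follow-up or withdrawing consent. Nothing in the documents shows that.

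**Conclusion.** The point holds as a partial bypass. As written, the rule sends tralokinumab subjects with a treatment-related stop and some other Week 12 data to MAR, and so weakens the plan's only departure from MAR. It does not disable the placebo-based step: subjects with no other Week 12 data still reach it.

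The number affected is unknown. For an assumed k of 1 to 4 out of 40, the sensitivity estimate stays near 3.50-fold where the SAP's own placebo-based step would give 3.39 to 3.09. This rests on the assumed k, on fully placebo-like imputed values and on treatment being in the imputation model.

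It would be wrong to infer that the primary result is biased by this rule. The primary complete-case ANCOVA does not use it, and only this sensitivity analysis is affected. The rule should still be changed, because the present order works against the section's stated purpose and the correction is simple.

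**What to change.** Put the reason first in SAP 4.1.1. Any tralokinumab subject with a missing Week 12 biopsy who permanently stopped IP or left the study for reasons (1)-(4) is imputed from placebo, whatever other Week 12 data exist. All other missing biopsies are imputed under MAR, as the SAP already states.

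The outcome then no longer depends on how other Week 12 data are defined, and no field recording why a bronchoscopy was not done is needed. One consequence should be accepted openly: a subject who stopped for reasons (1)-(4) and whose later specimen failed is also imputed from placebo.

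The cost is one SAP sentence and a programming rule using the discontinuation reasons already collected for disposition (SAP 4.2.1, protocol 3.9.2). The sensitivity estimate may become slightly less favourable.
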